8.0 Recruitment Methods

ARMS 1, 2, and 3

IRB approved flyers will be distributed to the residents at each of the Humanities Foundation apartment complexes as well as posted in general public community areas. Educational sessions, headed by the PI, will also be held at the complexes to allow potential participants to learn about the program and ask pertinent questions. Individuals who are interested in the program will be directed to contact the study PI or their designee via phone or at the information sessions. If interested participants meet the eligibility criteria and voluntarily consent to join the study they will be enrolled.

Additionally, we will recruit individuals who have had recent services through MUSC ED that have authorized research contact permission in MyChart through the MUSC electronic 'opt in' EPIC designation and have been identified by the Bioinformatics Center (BMIC) as over 60 years old, have had a recent fall and reside at one of the Humanities Foundation complexes. We will then contact potentially eligible patients by telephone to determine if they are interested in participating in the study and if so, schedule an informed consent meeting.

Supplemental ARM 4:

All CGs will be recruited through local affiliations with social and medical Respite Care Centers (RCC) and home health services for families of PWD established through our Mealtime Partnerships R01 study. We will devise and use IRB approved study recruitment flyers and letters that will be disseminated electronically and handed to RCC caregivers, as well as directly contact CGs by phone that have previously expressed and noted their agreement to be contacted regarding other research studies as documented on their consent form. In addition, we will conduct outreach activities and engage outside network RCC providers in the local community to inform them of the opportunity for their clients to participate in this study.

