From the initial screening of participant by inclusion and exclusion criteria to the informed consent process to the provision of participant study instruction to staff training in Good Clinical Practices (GCP) and regulations pertaining to the Conduct of Human Participant Research to study contact with participants to internal monthly quality control audits and protocol fidelity monitoring to the real-time review of AE by the ISM to the oversight of MUSC's IRB, procedures for monitoring study safety are consistently afforded throughout study. Specific procedures include:

- Participants will be screened for inclusion and exclusion per the protocol; the PI shall verify 100% of participants' eligibility prior to study enrollment through review of inclusion and exclusion criteria with potential participants.
- Participants will be fully informed as to all known risks and the possibility of risk from study participation in the informed consent process. **These risks are minimal.**
- Participants will be instructed to notify the researchers of any/all suspected or experienced adverse events whether they believe them to be related or not to the intervention.
- All reported participant AEs will be tracked through to resolution.
- All investigators and researchers will maintain active CITI Human Subject Research and Good Clinical Practice training.
- The PM will conduct a monthly internal quality control audit of all participant records to ensure compliance with MUSC IRB regulations; the PI and Program Coordinator (PC) will work together to correct any errors.
- The PI and/or designee will observe and evaluate ten (10%) percent of eligibility screening visits, informed consents and study instructions performed by IRB approved study personnel and provide feedback and/or retraining of study personnel if fidelity to both applicable federal regulations and the protocol is not observed.
- The BS will generate semi-annual AE reports for the PI and SMC to review.
- The ISM will have access to real-time study data and will be able to provide immediate recommendations to the PI.
- Investigator performance and compliance will be provided for through MUSC IRB and ORI study oversight.

2) Minimizing Research-Associated Risk

Diligent study safety monitoring will be conducted by all member of the research team and the SMC throughout the conduct of this study in compliance with the following required elements of MUSC IRB's continuing review process:

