1) Identifying. Potential minimum risks identified for participants are outlined in the Protection of Human Participants and will also be outlined in the IRB-approved informed consent document. Additional unknown risks may occur and, if so, will be identified through diligent monitoring by the PI or PC throughout the conduct of this study. During the informed consent process, participants will be advised of the potential risks of participation as identified in the IRB-approved informed consent document and reminded throughout the study that the researchers should be promptly informed about any concerns regarding potential side effects, adverse events, or clinical deterioration. Participants will also be instructed to notify the PI, PC, and/or designee of any suspected adverse events immediately if possible. The PI or PC will maintain an electronic record of all reported adverse events and notify the ISM of all reportable events as they occur. The ISM will have real-time access to the study database to review and monitor all reported SAE that were reported as related to the intervention. Additionally, the BS will generate and provide de-identified cumulative administrative human participant semi-annual safety reports for the ISM and SMC to review.

2) Reviewing. Adverse events will be initially be assessed and graded by PM and then reviewed by the members of the SMC according to the following MUSC's IRB Adverse Event Reporting Policy [http://academicdepartments.musc.edu/research/ori/irb/HRPP/HRPP Guide Section 4.7](http://academicdepartments.musc.edu/research/ori/irb/HRPP/HRPP%20Guide%20Section%204.7)

- **Expected/Anticipated**—Identified in nature, severity, or frequency in the current protocol, informed consent, investigator brochure, or with other current risk information.
- **Unexpected/Unanticipated**—Not identified in nature, severity, or frequency in the current protocol, informed consent, investigator brochure, or with other current risk information.
- **More Prevalent**—Occurs more frequently than anticipated or at a higher prevalence than expected.
- **Serious**—Results in death, is life threatening, requires inpatient hospitalization or prolongs existing hospitalization, results in persistent or significant disability/incapacity, cancer, overdose, or causes a congenital anomaly/birth defect.

The relationship of adverse events to study participation will be determined by the SMC according to the MUSC IRB Adverse Event Reporting Policy:

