4) Examples of Potential Reportable Adverse Events: In accordance with MUSC IRB Adverse Event Reporting Policy, an AE is reportable if it meets all of the following criteria: 1) is unexpected 2) is related and/or possibly related, and 3) is serious and/or suggests that the research places subjects or others at a greater risk of physical or psychological harm than was previously known or recognized. Additionally, per MUSC's policy all participant deaths, protocol deviations, complaints about the research, and breaches of confidentiality are reportable events. An example of an AE would be new onset chest pain and discomfort (symptom) that could potentially be associated with increased physical activity. The participant's parent reported he/she recently ran out of his/her medication. The steps to be taken include withdrawing the subject from the study and inviting him or her to restart the study after symptoms subside. An example of an SAE would be the death of a participant from acute chest syndrome or stroke, which although would be viewed as unexpected and unrelated to the intervention is nonetheless a reportable serious event. No further steps would be taken except to review, grade and report the event. An example of an unanticipated problem would be the participant trips and falls while participating in the exercise program. The steps in this case would be to report the event as per the IRB and NINR policy, and to discuss appropriate actions regarding whether the participant should remain in the study with the ISM and SMC. These events and problems will be reported in accordance with the IRB and NIH/NINR policy as noted in Section C.3.

SECTION D. Multi-site Monitoring and Compliance

This is not a multi-site study.

SECTION E. Assessment of External Factors

The PI will conduct a semi-annual assessment of external factors through a review of literature related to new developments in the areas of self-management and symptom management of chronic pain and/or fatigue, symptom reporting and other approaches that may have an impact on the safety of participants or on the ethics of the study.

SECTION F. Interim Analysis

This study aims to test the feasibility of a multi-component, technology-based intervention to promote self-management and symptom management of chronic pain and fatigue among low-income older adults. To our knowledge, there are no similar interventions specifically designed for this patient

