Project Director, (PD). **[name]** is a Research Associate at the College of Nursing at MUSC. [name] will be responsible for the classification of all reported adverse events (AE) and for ensuring that all serious adverse events (SAE) are forwarded to the PI, C, and IRB, and in compliance with MUSC IRB and NIH's reporting requirements. In addition, and in conjunction with the PI, the [name] will be responsible for amending the protocol in accordance with the SMC's recommendations, submitting reportable SAEs to the IRB, and submitting annual SMC reports to the IRB and NIH. As part of the SMC, he will be responsible for: conducting internal quality control audits on all participant records and notifying the PI of any deficiencies; assisting in the generation of ad hoc participant data safety reports; and, forwarding reportable SAE to the NIH/NINR Program Official through MUSC's OSRP within 72hrs of IRB review and acknowledgement. [name] will also be responsible for following up on reported AEs to monitor outcomes and provide for the continuity of care for participants.

SECTION B. Procedures for Safety, Risk and Confidentiality

1) Monitoring Study Safety

From the initial screening of study participants by inclusion and exclusion criteria to the informed consent process to the provision of participant study instruction to staff training in Good Clinical Practices (GCP) and regulations pertaining to the Conduct of Human Participant Research to regularly scheduled study contact with participants to internal quality control audits and protocol fidelity monitoring to the real-time review of AEs, and to the oversight of MUSC's IRB - procedures for monitoring study safety are consistently afforded throughout study. Specific procedures include:

- All participants will be screened for inclusion and exclusion per the protocol
- All participants will be fully informed as to all known risks and the possibility of risk from study participation in the informed consent process. **These risks are minimal.**
- AEs and changes in medical status will be elicited at every participant visit and contact.
- All participants will be given a 24 hrs. AE reporting phone number and will instructed to notify the researchers of any/all suspected or experienced adverse events whether they believe them to be related to the intervention or not.
- The PD will track all reported participant AEs through to resolution. Please see Section C. 1 – 4.

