15.0 Risks to Subjects

The risks associated with this intervention are not considered greater than those that patients would otherwise be exposed to when engaged in an routine physical activity exercise program. Overall, potential risks associated with participation in the study are viewed to be minimal. However, as with all studies, there are inherent risks involved with the conduct of human subject research that gathers Protected Health Information (PHI). Participants will be made aware of these risks during the Informed Consent process. Identified study risks include: Physical discomfort, emotional distress, social wellbeing, Loss of privacy, and randomization.

Physical discomfort. Participants with pre-existing medical conditions that would make increase in physical activity dangerous to their health will be excluded from the study. There may be minor physical discomfort from the increase in physical activity; however, the potential risk to all subjects is minimal. The participants' pain and fatigue scores will be assessed on a weekly basis by the PI, who is a Board-Certified Family Nurse Practitioner, which will allow for further determination of any untoward effects of participation in the physical activity program. The PI will be communicating with the participants via telehealth visits on a weekly basis to allow for further follow-up of any physical issues with the program.

Emotional distress. Participants will be asked to provide information about their self-reported pain and fatigue, social isolation, depression and demographic data. These questions pose an anticipated low psychological risk, e.g. for anxiety, if participants appear upset by questions about their health issues, they will be instructed that if they do not wish to answer a question, they can skip it and go to the next question.

Social well-being. There is low potential for adverse social effects in this research study. Through bi-weekly telehealth visits with nurses, participants will have social support during their participation.

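### Falls are missing from the listed risks and an exercise fall is labelled unanticipated, although the protocol treats falls as foreseeable; Arms 1-3 also have no scheduled adverse-event or falls question

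*Protocol*

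**What the plan says.** **Classification.** The Arms 1-3 safety plan (Protocol 13.0, Section C.4) states: "An example of an unanticipated problem would be the participant trips and falls while participating in the exercise program". Such an event is to be reported under IRB and NINR policy, and the participant's continuation discussed with the independent safety monitor (ISM) and the Safety Monitoring Committee (SMC). Section C.2 defines an unanticipated event as "Not identified in nature, severity, or frequency in the current protocol, informed consent, investigator brochure, or with other current risk information".

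**Listed risks.** Section 15.0 reads: "Identified study risks include: Physical discomfort, emotional distress, social wellbeing, Loss of privacy, and randomization". It describes the physical risk as follows: "There may be minor physical discomfort from the increase in physical activity; however, the potential risk to all subjects is minimal".

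**Recruitment.** Besides flyers and information sessions, Section 8.0 adds an emergency-department route for people over 60 who "have had a recent fall and reside at one of the Humanities Foundation complexes".

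**Ascertainment.** For Arms 1-3, Section B.1 says: "Participants will be instructed to notify the researchers of any/all suspected or experienced adverse events". For Arm 4, the corresponding section says: "AEs and changes in medical status will be elicited at every participant visit and contact".

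**The concern.** The protocol appears to hold two positions on the same hazard. Its rationale, one recruitment route and its exercise instructions treat falling as something to expect. Its risk section does not mention falls, and its safety plan calls an exercise fall unanticipated. Under the protocol's own definition, that label depends on falls having been left off the risk list.

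The second part is ascertainment. The arms doing strength and balance exercise, some of whose participants may be recruited after a fall, have the less specific procedure. The yoga-only caregiver arm has scheduled elicitation. Events that participants must volunteer are more easily missed than events they are asked about. The two yoga arms also have a weekly instructor-led group session that the Otago-only arm lacks, so there may be more occasions to mention an event. Differences between arms in volunteered events would then be hard to interpret.

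At stake is the safety information this pilot carries forward. Section 13.0 F (Arms 1-3) says that safety will be evaluated and used in designing a larger trial.

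**Working it through.** No arithmetic applies: the documents state no fall rate, expected event count or figure to reproduce. The check sets the passages side by side.

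**Step 1. Is a fall foreseeable on the protocol's own text?** Yes, in four places.
- Section 1.0: pain and fatigue in older adults are said to raise the risk of falling.
- Section 2.0: Otago is presented as a fall-prevention programme.
- Section 8.0: one recruitment route selects on a recent fall. A recent fall is not an inclusion criterion in Section 5.0, and the share of participants entering by this route is not given.
- Section 10.0, Table 1: participants are observed for their ability to regain balance before exercising without support, and some are expected to be unstable at the start.

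**Step 2. Do the safety sections reflect this?** No. None of the five risks in Section 15.0 is a fall or an injury.

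**Step 3. Is the label consistent with the definition?** Not cleanly. Section C.2 makes an event unanticipated if the protocol, consent form or other risk information does not identify it. Section C.4 itself names the exercise fall in the protocol. Sections C.2, C.4 and 15.0 therefore need reconciling.

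**Step 4. What does the label do in practice?** Section C.4 makes an adverse event reportable only if three conditions all hold: it is unexpected; it is related or possibly related; and it is serious or suggests greater risk than previously known. If falls were simply moved to the anticipated list, a non-serious exercise fall would fail the first condition. The relabelling cannot safely be done alone.

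**Step 5. How would a fall come to light in Arms 1-3?**
- Specific procedure: participants notify the team (B.1), and are reminded to do so during the study (C.1).
- General commitment: B.2 promises continuing solicitation of adverse events, but names no method, interval or falls item.
- Weekly contact: Section 15.0 has weekly telehealth visits at which physical problems can be followed up. The weekly row of Table 2 covers diary entries, pain, exercise progress, fatigue and sleep.
- Outcome schedule: Table 2 has a chair-stand test, a balance test and a walk test, but no fall count or fall diary.
- Analysis: the biostatistician tabulates type, frequency and outcome of documented adverse events twice a year (A.2). The SAP has no adverse-event or falls analysis.
- Follow-up: no weekly contact is described between week 12 and the 3-month visit.

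**Step 6. Compare Arm 4.** Both B.1 and C.1 of the Arm 4 plan have the researchers ask about adverse events at each contact. The wording needed for Arms 1-3 already exists in the same protocol.

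**The case against.** The strongest reply is that the safety system is broader than the notification sentence suggests. The Arms 1-3 plan commits to soliciting adverse events, provides weekly contact, tracks reported events to resolution and tabulates them. Section 15.0 also says that people for whom more activity would be dangerous are excluded, and emergency contacts are given to everyone. The present label even raises the visibility of an exercise fall, because it sends the event to the ISM, the SMC and the IRB. Finally, falls are not an outcome in the aims, Table 2 or the SAP, so asking for fall data could be called an extension of scope.

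Much of this stands, and it limits the point in three ways.
- A reader might infer that participants are not told about falls. The documents do not show that. Section C.1 places the risks in the consent document and in a human-participants section, and neither is available here. The definition in C.2 hints that falls are absent from the consent form, but that is inference.
- A reader might infer that falls are not actively counted at all. The general solicitation, weekly contact and semi-annual tabulation contradict that. What is missing is a scheduled question and a falls item.
- A reader might want a number of falls expected or missed. Any such figure would rest on an assumed annual rate, and the point does not need one.

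The scope argument does not remove the point. Asking about adverse events is safety monitoring, which the protocol undertakes to do, and it asks more systematically in Arm 4. The argument about the label does not defend the omission from Section 15.0; it shows what must be kept when the label is corrected.

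**Conclusion.** The point holds as a defect of consistency and of ascertainment. The protocol's rationale, recruitment and exercise instructions treat falls or loss of balance as foreseeable, while Section 15.0 omits them and Section C.4 calls an exercise fall unanticipated. Arms 1-3 have no scheduled adverse-event or falls question, whereas Arm 4 asks at every visit and contact.

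It touches all 30 participants in Arms 1-3, planned as 10 per arm. Its effect on event counts is unknown. Under-ascertainment is a reasonable expectation from reliance on notification, but it is not demonstrated. The conclusion assumes that no unavailable document schedules such a question for Arms 1-3. It does not bear on the validity of the feasibility or symptom outcomes. It is a safety improvement worth making, chiefly because it costs little.

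**What to change.** 1. List falls as a foreseeable risk in Section 15.0 and check that the consent form does the same.
2. Reconcile Section 15.0 with Sections C.2 and C.4 of the Arms 1-3 safety plan. In the same amendment, state explicitly that exercise-related falls are still reported to the ISM, the SMC and the IRB. Steps 1 and 2 must be made together, for the reason in Step 4 of the check.
3. Apply the Arm 4 elicitation wording to Arms 1-3: one scripted adverse-event and falls question at each existing weekly telehealth visit, at the week-12 visit and at the 3-month visit. The 3-month question should cover the interval since week 12.
4. Add to the SAP a descriptive table of falls and adverse events by arm.

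The SAP is written in the past tense. If data collection is over, report the recorded falls and adverse events by arm, state how they were ascertained and the limit this sets, and carry items 1 to 3 into the successor protocol.

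The cost is risk and consent wording, one question at contacts already held, and one table. More non-serious events will be recorded, and readers should expect that when comparing with studies that rely on notification. The management of individual falls is left to the sponsor.

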15.0 Risks to Subjects

The risks associated with this intervention are not considered greater than those that patients would otherwise be exposed to when engaged in an routine physical activity exercise program. Overall, potential risks associated with participation in the study are viewed to be minimal. However, as with all studies, there are inherent risks involved with the conduct of human subject research that gathers Protected Health Information (PHI). Participants will be made aware of these risks during the Informed Consent process. Identified study risks include: Physical discomfort, emotional distress, social wellbeing, Loss of privacy, and randomization.

Physical discomfort. Participants with pre-existing medical conditions that would make increase in physical activity dangerous to their health will be excluded from the study. There may be minor physical discomfort from the increase in physical activity; however, the potential risk to all subjects is minimal. The participants' pain and fatigue scores will be assessed on a weekly basis by the PI, who is a Board-Certified Family Nurse Practitioner, which will allow for further determination of any untoward effects of participation in the physical activity program. The PI will be communicating with the participants via telehealth visits on a weekly basis to allow for further follow-up of any physical issues with the program.

Emotional distress. Participants will be asked to provide information about their self-reported pain and fatigue, social isolation, depression and demographic data. These questions pose an anticipated low psychological risk, e.g. for anxiety, if participants appear upset by questions about their health issues, they will be instructed that if they do not wish to answer a question, they can skip it and go to the next question.

Social well-being. There is low potential for adverse social effects in this research study. Through bi-weekly telehealth visits with nurses, participants will have social support during their participation.

Loss of privacy. PHI from participants will be gathered and stored electronically on secure and encrypted servers and there are risks associated for the loss of privacy and confidentiality. As well as having a comprehensive DSMP that details data safety, handling, monitoring, storage and security procedures, we will further minimize the potential for loss of confidentiality through the physical separation of participant names from their research record.

All participants will be screened for depression using the PROMIS Emotional Distress-Depression Short Form 8a. If a participant scores in the severe depression category (raw score 33 and above) a referral will be placed to a mental health professional which could result in loss of confidentiality. Additionally, participants that score in the moderate depression category (raw score 23 to 32) further screening for suicidal ideation will take place. If the participant would admit to suicidal ideation at any time during the study, an emergent mental health consult will be placed which could also lead to loss of confidentiality.

Randomization. Participants are being assigned to one of three study groups and treatment programs by chance. Each exercise program may prove to be less or more effective or have more or less or unknown side effects than the other or other available treatments. Participation in the study is completely voluntary and participants may withdraw their consent at any time.

If participants should experience any symptoms during physical activity and medical attention is needed, resource numbers of local healthcare providers and hospital system emergency services are provided to all subjects to access in the same manner they would with any emergency that they encountered. The PI is a board-certified Family Nurse Practitioner and will be available as a resource by telephone during regular business hours. This information (contact resources) is provided in writing to all subjects who choose to consent and enroll in the study.

